5.5.3 Temozolomide

5.5.3.1 Dose modifications of temozolomide during concomitant treatment

During the concomitant treatment, **no dose reductions** will be made. Delay and discontinuation will be decided according to toxicity criteria and the relationship to the study drug as defined hereunder. In case of toxicity related to temozolomide, the following actions should be taken.

Please note that the delay may not exceed 2 weeks, if toxicity is ongoing at that time, concomitant treatment with temozolomide must be discontinued.

Although most of the toxicities caused by temozolomide will be of hematological origin, according to previous studies non hematological events could be expected too: nausea and vomiting, fatigue, infections, hepatic function disturbances and rash.

Averse Drug Reaction	Value	CTCAE Grading Version 3.0	Action
Haematological			
ANC	≥ 0.5 and $< 1.5 \times 10^9/L$	2-3	Delay TMZ1 until normalization
ANC	$< 0.5 \times 10^9/L$	4	Stop concomitant TMZ
Platelets	≥ 25 and $< 75 \times 10^9/L$	2-3	Delay TMZ until normalization
Platelets	$< 25 \times 10^9/L$	4	Stop concomitant TMZ
Non haematological			
Except fatigue, alopecia, nausea and vomiting*		2	Delay TMZ until normalization
Except fatigue, nausea and vomiting*		3-4	Stop concomitant TMZ

* For Nausea and vomiting; please refer to section 5.6.

1 temozolomide

5.5.3.2 Dose modification of temozolomide during the adjuvant treatment

During adjuvant treatment temozolomide dose interruptions as well as modifications are allowed.

Dose modifications are based on toxicity observed during prior treatment cycle. If multiple toxicities are seen, the dose administered should be based on the dose reduction required for the most severe grade of any single toxicity.

The possible doses of temozolomide are as follows:

Dose level	Dose mg/m ² /day (1-5)	Action
-1	100	Reduction if prior toxicity
0	150	Starting dose cycle 1
+1	200	Escalated dose as of cycle 2 in absence of toxicity

The first cycle of temozolomide is administered at the dose of 150 mg/m² d1-5. The dose is escalated at 200 mg/m² /day as of cycle 2 in absence of toxicity.

- Dose reduction according to worst adverse drug reaction during previous cycle

Adverse drug reaction	Value	CTCAE grading Version 3.0	Action
Haematological			
ANC and Platelets	≥ 1.5 x 10 ⁹ /L	0-1	Escalation to Dose Level +1 (only at cycle 2) ☐ or continue at current dose
	≥ LLN	0	
ANC and Platelets	≥ 1 and < 1.5 x 10 ⁹ /L	2	Dose unchanged
	≥ 50 and <LLN	1-2	
ANC and/or Platelets	< 1 x 10 ⁹ /L	3-4	Reduce by 1 dose level
	< 50 x 10 ⁹ /L	3-4	
Non haematological toxicity			
Except fatigue, alopecia, nausea and vomiting*		0-2	Escalation to Dose Level +1 (only at cycle 2) ☐ or continue at current dose
Except fatigue, nausea and vomiting*		3	Reduce by 1 dose level
Except fatigue, nausea and vomiting*		4	Stop treatment

☐ the dose of temozolomide may only be increased from 150 mg/m²/day to 200 mg/m²/day as of cycle 2.

* For nausea and vomiting, please see section 5.6.

A **maximum of 2 dose reductions** is permitted. However, if the same (in nature and severity) non haematological toxicity occurs at 2 subsequent cycles despite 1 dose reduction, a second dose reduction is not permitted and the patient should stop the treatment. **No dose reductions below 100 mg/m² are**

allowed, if 100mg/m² is not tolerated the patient should stop treatment. Once a dose has been reduced, **no dose re-escalation** is allowed.

- Treatment delay according to worst adverse drug reaction during previous cycle

Adverse Drug Reaction	Value	CTCAE Grading Version 3.0	Action
Haematological			
ANC	< 1.5 x 10 ⁹ /L	2-3-4	Delay up to 2 weeks until resolution to at least grade 1. If unresolved then stop
and/or Platelets	< 75 x 10 ⁹ /L	2-3-4	
Non haematological toxicity			
Except fatigue, alopecia, nausea and vomiting*		2-3	Delay up to 2 weeks until resolution to at least grade1. If unresolved then stop
Except fatigue, nausea and vomiting*		4	Stop treatment

- For nausea and vomiting, please see section 5.6. Summary of initial dose and schedule

5.6 Concomitant medications

- Prophylactic antiemetics will be administered at the discretion of the treating physician. The prophylactic use of a 5-HT-3 antagonist is strongly recommended before the adjuvant temozolomide administration, **especially on day 1-3 and should be taken 1 hour before temozolomide is administered**. During radiotherapy with concomitant daily dose of temozolomide antiemetic prophylaxis is usually not necessary, but may be considered on the first three days.
- Corticosteroids are administered at the treating physician's discretion, but the dosage should be kept as low as possible.
- Pneumocystis carinii prophylaxis is mandatory during radiotherapy-daily temozolomide concomitant treatment. Corticosteroid therapy and continuous temozolomide therapy induce lymphocytopenia. Patients are therefore at an increased risk of opportunistic infections. Therefore a prophylaxis against Pneumocystis carinii pneumonia is mandatory. It can be either pentamidine inhalations once every 4 weeks or trimethoprim-sulfamethoxazole 960 mg 3 times a week. Prophylaxis should be continued during the entire concomitant treatment or until patients have recovered from lymphocytopenia to at least grade 1.

5.7 Prohibited medications

- No other investigational treatment should be used.
- No other anti-cancer agents.
- No growth factors unless it is vital for the patient.

6 Clinical evaluation, laboratory tests and follow-up

6.1 Immediately post-surgery: registration step

For the submission of tumor material for pre-randomization 1p/19q analysis (or review) and MGMT analysis, all patients must be registered at the EORTC Headquarters as soon as possible, and material must be sent as soon as possible, as follows:

- Submission of paraffin tumor blocks or 30 unstained sections for central pathology review, for 1p/19q LOH, and for determination of MGMT promoter methylation
- Submission 20 ml whole blood collected in EDTA tube for assessment of LOH 1p/19q

6.2 Before treatment start: randomization step

All pretreatment physical, neurological and quality of life evaluations should be performed within 2 weeks of randomization but after the surgical procedure leading to the diagnosis of anaplastic glioma. All laboratory evaluations must be carried out within 4 weeks from randomization. The initial assessment of disease with MR or CT must be performed between the surgery and the start of radiotherapy, unless patients underwent a biopsy only in which case the pre-operative imaging is sufficient (and only a CT for radiotherapy planning is required). Radiotherapy and concomitant temozolomide should be started within 8 days of randomization.

The baseline evaluations include:

- Complete medical history
- Physical examination including neurological evaluation and vital signs
- Vital signs, blood pressure, height and weight
- WHO-ECOG performance status
- Mini mental status examination (MMSE)
- Quality of Life C30 and BCM20
- Corticosteroid intake
- Complete blood counts: hemoglobin, haematocrit, white blood cells and differential, platelets.
- Serum chemistry: sodium, potassium, calcium, creatinine, urea, glucose, ASAT, ALAT, total bilirubin, alkaline phosphatase, gamma-GT, total protein, LDH.
- Toxicity according to CTCAE v.3
- Gadolinium enhanced MRI or contrast enhanced CT scan of the brain
- Fresh frozen tumor material for translational research (optional)
- Cognitive exam (dedicated centers only)

6.3 During radiotherapy treatment

6.3.1 During radiotherapy with or without concomitant temozolomide treatment

Patients are seen on a weekly basis. A more detailed evaluation will take place at week 4, week 6 (= end of radiotherapy) and 4 weeks after the end of radiotherapy. Patients treated with temozolomide during radiotherapy require monitoring for side-effects, particularly hematotoxicity.

6.3.1.1 Weekly visits

- Physical examination including vital signs
- Complete blood count (**temozolomide patients only**)
- Toxicity according to CTCAE v.3

6.3.1.2 Evaluation at week 4 and 6

- Physical examination including vital signs and neurological evaluation
- WHO-ECOG performance status
- Toxicity according to CTCAE v.3
- Complete blood count, all serum chemistries including LDH (**temozolomide patients only**)
- Corticosteroids intake

6.3.1.3 Evaluation 4 weeks after the end of radiotherapy

- Physical examination including vital signs, and neurological evaluation
- Corticosteroid intake
- MMSE
- Quality of Life C30 and BCM20
- WHO-ECOG performance status
- Toxicity according to CTCAE v.3
- Complete blood count, all serum chemistries
- Gd-enhanced MRI or contrast CT scan of the brain
- Corticosteroid intake

6.4 After the end of radiotherapy

Patients are followed every six months for disease assessment; in addition patients randomized to receive adjuvant temozolomide are followed every four weeks prior to the start of the next cycle of temozolomide.

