5.2.2.4 Temozolomide dosing during adjuvant treatment

Patients randomized to adjuvant temozolomide will start adjuvant temozolomide after a 4 week resting period after the end of radiotherapy. Temozolomide will then be administered orally once a day for 5 consecutive days (days 1-5). The starting dose for the first cycle will be 150 mg/m²/day with a single dose escalation to 200mg/m²/day in subsequent cycles if no significant toxicity is observed in the first cycle. One cycle is defined as 28 days and a maximum of 12 cycles will be administered. Treatment can be discontinued earlier in case of significant toxicity interfering with further treatment and not responding to dose reductions, or at the patient wish.

The dose administered will be determined using the BSA calculated at the beginning of each treatment cycle. The dose will be rounded to the nearest 5 mg. In case of high value of BSA, an upper limit of 2.1 m² is suggested to calculate the dose. The exact dose administered should be recorded on the CRF. Each daily dose should be given with the least number of capsules. Patients should be instructed to fast 1 hour before and one hour after administration of temozolomide. Water is allowed during the fasting period. Patients should be told to swallow the whole capsules in rapid succession without chewing them. If vomiting occurs during the course of the treatment, no redosing of the patient is allowed before the next scheduled dose.

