6.4.1 Six monthly disease evaluation after the end of radiotherapy

All patients would have six monthly disease and status assessment after the end of radiotherapy.

- Physical examination including neurological evaluation
- Corticosteroid intake
- MMSE
- Quality of Life C30 and BCM20
- WHO-ECOG performance status
- Toxicity according to CTCAE v.3
- Gd-enhanced MRI or contrast CT scan of the brain
- Cognitive exam; dedicated centers only, to be carried out yearly after the start of radiotherapy (e.g., 12 months, 24 months, 36 months etc)

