6.4.2.1 Prior to each cycle of adjuvant therapy

- Physical examination including vital signs
- WHO-ECOG performance status
- Toxicity according to CTCAE v.3
- Complete blood count, all serum chemistries

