6.5 After the documentation of first progression

The patient must be followed every six months, in particular for performance status, quality of life, cognition and for documentation of further treatments.

- Physical examination including neurological evaluation
- Corticosteroid intake
- MMSE
- Quality of Life C30 and BCM20
- WHO-ECOG performance status
- Documentation of further treatments

All patients will be followed until death.

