7.1.2.2 Clinical /neurological progression

Clinical/neurological progression is defined as the presence of the following conditions:

- decrease in WHO performance status
 - for patients with baseline WHO performance status 0: deterioration to WHO performance status 2 or worse for which no other explanation is present
 - for patients with baseline WHO performance status 1 or 2: deterioration to WHO performance status 3 or worse for which no other explanation is present
- deterioration of neurological functions
- appearance of signs/symptoms of increased intracranial pressure (headache, nausea and vomiting without other explanations)
- and/or start of corticosteroid or increase of corticosteroid dosage by 50% for control of neurological signs and symptoms

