7.2 Neurological deterioration free survival

This study will assess neurological deterioration as a secondary endpoint to investigate if the prolongation of progression free survival translates into a better preservation of neurological function. Neurological deterioration is defined as a decrease in WHO performance status as follows:

- decrease in WHO performance status
 - for patients with baseline WHO performance status 0: deterioration to WHO performance status 2 or worse for which no other explanation is present, and which is maintained for at least three months
 - for patients with baseline WHO performance status 1 or 2: deterioration to WHO performance status 3 or worse for which no other explanation is present and which is maintained for at least three months

The date of neurological deterioration will be the first date the persistent decrease in performance status was diagnosed. Neurological deterioration free progression is the time interval between the date of randomization and the date of neurological deterioration or death whichever occurs first. If neither event has been observed, the patient is censored at the date of the last follow up examination.

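### Performance status is checked four-weekly in the adjuvant arms but six-monthly in the others, so PS-based events in the adjuvant year are dated earlier there: a small, conservative bias that needs a sensitivity analysis

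*Combined protocol and SAP*

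**What the plan says.** All references are to the combined protocol and SAP.

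- **Common schedule.** PS is recorded at weeks 4 and 6 of radiotherapy and 4 weeks after it (6.3.1.2, 6.3.1.3). Then "All patients would have six monthly disease and status assessment after the end of radiotherapy" (6.4.1), with PS and brain imaging at each visit.
- **Extra visits in arms 3-4.** Section 6.4 states: "in addition patients randomized to receive adjuvant temozolomide are followed every four weeks prior to the start of the next cycle of temozolomide". Section 6.4.2.1 lists "WHO-ECOG performance status" before every cycle, but no imaging, neurological evaluation or steroid record. On length, 5.2.2.4 says: "One cycle is defined as 28 days and a maximum of 12 cycles will be administered". The summary table in 6.6 agrees.
- **After first progression, all arms.** "The patient must be followed every six months, in particular for performance status, quality of life, cognition and for documentation of further treatments" (6.5).
- **Dating rule.** Neurological deterioration is a PS fall with no other explanation, "which is maintained for at least three months" (7.2). Then: "The date of neurological deterioration will be the first date the persistent decrease in performance status was diagnosed".
- **Use in PFS.** The same thresholds appear as clinical progression in 7.1.2.2, for example "for patients with baseline WHO performance status 0: deterioration to WHO performance status 2 or worse for which no other explanation is present", without the persistence rule. Imaging confirmation is recommended, not required (7.1.2.3).
- **Analysis.** Sections 8.2.1.2 and 8.2.1.3 have no common-visit rule and no interval censoring. The only sensitivity analysis in 8.2.4.1 is per protocol.

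**The concern.** An event dated by when it is noticed depends on how often someone looks. For up to 12 cycles, arms 3-4 are looked at about six times as often as arms 1-2, and that split is exactly Question II. Two patients with the same decline on the same day can receive event dates months apart because of their allocation.

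Neurological deterioration-free survival is the endpoint section 7.2 offers to show whether longer PFS preserves function. A schedule that dates deterioration earlier under adjuvant temozolomide works against seeing that. The same applies to the part of PFS that comes from PS alone.

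**Working it through.** **The plan's own figure.** The plan gives no number on this point. Its design figure, 534 deaths, reproduces: Schoenfeld's formula, 4(1.960 + 0.954)² / (ln 0.775)², gives 523, and adding the 11 for the interim look gives 534. It concerns overall survival and does not depend on the visit schedule.

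**Timeline.** Radiotherapy starts within 8 days of randomization and lasts 6.5 weeks, so it ends at about week 6.5-7.5. The visit 4 weeks later, which is also about when cycle 1 starts, falls at week 10.5-11.5. The last of 12 pre-cycle visits is 11 × 4 = 44 weeks after that, at week 54.5-55.5. The first six-monthly visit is at about week 32.6-33.5 and the second at about week 58.7-59.5.

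**One patient.** A decline at month 4 (week 17.4, at 4.35 weeks per month) meets the next pre-cycle visit at week 18.5-19.5, or month 4.3-4.5. In arms 1-2 the next scheduled PS is at week 32.6-33.5, or month 7.5-7.7.

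**Mean delay.** With declines spread evenly between visits, the mean delay is half the interval:
- four-weekly: 28 / 2 = 14 days
- six-monthly: 182.6 / 2 = 91.3 days
- difference: 77.3 days, about 2.5 months

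**Null hazard ratio over full follow-up.** The time to deterioration and the share of declines found only at scheduled visits are not in the documents, so both are assumed and varied. The simulation used 60,000 patients per group, no true effect, exponential event times, uniform censoring at 30-90 months and all 12 pre-cycle visits attended. Monte Carlo error is about 0.006.

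| Assumed median (months) | All found at scheduled visits | Half | Quarter |
|---|---|---|---|
| 12 | 1.068 | 1.040 | 1.013 |
| 18 | 1.043 | 1.021 | 1.020 |
| 24 | 1.022 | 1.020 | 1.013 |
| 36 | 1.010 | 1.010 | 1.013 |

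The mean delay between months 2.4 and 12.5 was 0.44 months (adjuvant) against about 3.0 (no adjuvant). The effect fades with longer medians because fewer true declines fall in that window: 39% at a 12-month median and 17% at 36 months.

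A second model lets death intervene (assumed median 9 months from deterioration to death; 8,000 per group). Delays were 0.43 against about 2.6 months. With all declines found at scheduled visits, the 5-year hazard ratio was about 1.04-1.05 at medians of 12-18 months and about 1.00-1.02 at 24-36 months.

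**If PS was three-monthly.** Sections 8.2.3.4 (MMSE) and 10.3.1 (quality of life) mention a three-monthly visit that chapter 6 does not contain. If PS was taken then in all arms, the gap falls to about 46 − 14 = 32 days.

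**Which comparisons are exposed.** Question I sets arms 1 and 3 against arms 2 and 4, one adjuvant arm on each side, so it is largely balanced. Imaging is six-monthly in every arm. Death is not visit-dependent.

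**The case against.** The case for leaving the plan alone is that the bias is small, runs against the experimental treatment and touches only secondary endpoints. The simulations also lean towards a larger effect:

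- They give every adjuvant patient all 12 pre-cycle visits. Section 5.3 stops treatment at progression, toxicity or refusal, and after progression all arms are six-monthly.
- They ignore the conditions in 7.2. The three-month persistence rule can work the other way: four-weekly visits can reveal a recovery and remove an event that six-monthly visits would keep.
- The thresholds are severe (unable to work, or in bed or chair more than half the day, per Appendix B). Such patients may well present between visits, and 7.2 dates the event when diagnosed, not at a scheduled visit. The documents do not say how often this happens.
- For PFS, a PS fall is one item in a list joined by and/or, and 7.1.2.3 asks for other explanations if imaging shows no clear progression. No separate size for PFS can be derived.

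All of this stands as a limit on size. None of it removes the unequal schedule or reverses the direction of the detection delay. It also argues against overriding the 7.2 definition, which would discard diagnosed dates in the main analysis.

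**Conclusion.** The unequal schedule is real, and nothing in the analysis plan allows for it. PS-triggered events in the adjuvant year are dated earlier in arms 3-4, by about 2.2-2.6 months on average if declines are found only at scheduled visits. For Question II the null hazard ratio over full follow-up is about 1.00-1.07. It is smaller if patients present between visits, stop adjuvant treatment early or had three-monthly PS. This rests on assumed medians of 12-36 months and exponential event times.

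A reader might infer that the schedule makes a null effect look like marked early harm. Cutting the no-effect model (15,000 per group, all declines found at scheduled visits) at week 59 does give hazard ratios of 1.42 and 1.46 for medians of 12 and 18 months. If half present unscheduled, the week-59 figure is about 1.2. But the second common visit in that model is at 7.5 + 52 = 59.5 weeks, so the cut falls half a week before arms 1-2 are next assessed. At week 60 the ratios are 1.09 and 1.07, with event counts nearly equal (8218 v 8220; 6214 v 6261), and about 1.04 if half present unscheduled. No 13-month analysis is planned: 8.2.3.2 specifies Cox models, medians and 5-year rates, for overall survival and PFS.

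Nor can the schedule manufacture an adjuvant benefit through earlier detection, or affect the primary endpoint. This is a cheap improvement to two secondary endpoints, not a flaw in the trial's main conclusion.

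**What to change.** Keep the 7.2 definition for the main analysis. Add to 8.2.4.1 a sensitivity analysis for Question II covering neurological deterioration-free survival, and PFS for progression that is clinical only. In every arm, do one of the following:

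- assign each such event, including those found at pre-cycle or unscheduled visits, to the next visit common to all arms (4 weeks after radiotherapy, then six-monthly); or
- treat it as interval-censored between common visits.

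Keep death dates as observed, so a death before the next common visit counts on its own date. Name the model for neurological deterioration-free survival, because 8.2.3.2 gives methods only for overall survival and PFS. Reconcile the three-monthly visits in 8.2.3.4 and 10.3.1 with chapter 6, and state whether PS was recorded at them.

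The cost is a paragraph of SAP text and one extra run on data already collected. Appendix M says all patients have completed treatment, so an analysis rule is the only remedy left for that phase. The downside is coarser event dates in that analysis, by up to six months. Section 8.3.2 records advice to release the adjuvant results on all endpoints. If they have been seen, the addition should be dated and labelled accordingly.

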6.4.1 Six monthly disease evaluation after the end of radiotherapy

All patients would have six monthly disease and status assessment after the end of radiotherapy.

- Physical examination including neurological evaluation
- Corticosteroid intake
- MMSE
- Quality of Life C30 and BCM20
- WHO-ECOG performance status
- Toxicity according to CTCAE v.3
- Gd-enhanced MRI or contrast CT scan of the brain
- Cognitive exam; dedicated centers only, to be carried out yearly after the start of radiotherapy (e.g., 12 months, 24 months, 36 months etc)

6.4.2 During adjuvant temozolomide treatment

Patients randomized to adjuvant temozolomide will receive twelve cycles of adjuvant temozolomide, unless treatment needs to be discontinued earlier. In addition to the disease assessments, patients will be followed during this phase as indicated hereunder:

